5.4 Rationale

Prompt diagnosis of hypoglycaemia is important as, untreated, it can lead to weight gain, symptomatic hypoglycaemia and increases the risk of sudden death through arrhythmia. At present, diagnosis of hypoglycaemia depends upon the reporting of symptoms and capture of hypoglycaemic range CBGs through finger prick glucose measurement. If the clinical suspicion of hypoglycaemia is strong enough, then patients will be admitted for a supervised 72 hour fast, where blood glucose is checked regularly through finger prick measurements and venous phlebotomy. Patients can lose hypoglycaemic awareness, however, and so symptoms are not always a reliable way to diagnose the problems. 72 hour fasts are labour intensive for the medical and nursing teams and may require the patient to take time off work or away from caring duties. A robustly tested CGM test may allow us to determine if blinded CGM testing can be used to obviate the need for inpatient testing. It may also provide useful diagnostic information by relating the proximity of hypoglycaemic episodes to food intake, adding to weight to diagnoses of reactive or spontaneous hypoglycaemia.

CGM has revolutionized the lives and medical management of type 1 Diabetes patients with hypoglycaemic unawareness and we hope that it can produce similarly excellent results in the field of reactive/spontaneous hypoglycaemia.

Once spontaneous hypoglycaemia has been diagnosed, treatment with medical therapy is often the first step. The goal is to try and make the patient hypoglycaemia free. This is tricky if the patient has no hypoglycaemia awareness, but can be overcome during the day with regular fingerprick glucose checks – though patients frequently complain that this is painful. At night, however, patients are asleep and

cannot check their blood glucose this way and so there is a paucity of data about their glycaemic state at night – the very time that they are fasting and hypoglycaemia is more probable. CGM can therefore tell us about their glycaemic status all day, without painful finger prick testing and also during the night whilst the patient is asleep. This information can then help doctors titrate their anti-hypoglycaemia medication with the aim of abolishing their hypoglycaemic episodes.

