6.1 Primary objective

- 1) Use CGM (blinded to the patient and investigator) in advance of standard investigations (where possible) in order to record whether patient symptoms correlate with recorded hypoglycaemia. This may exclude hypoglycaemia as a cause of symptoms and allow the patient to avoid a prolonged inpatient investigation.
- 2) Use CGM technology (blinded to the patient and investigator) alongside standard investigations for patients with both reactive and spontaneous hypoglycaemia to evaluate the relative efficacy of the two methods in detecting hypoglycaemia episodes.
- 3) Use CGM (blinded to the patient and investigator) to record frequency of hypoglycaemia after medical treatment has been initiated in order to assess its

effectiveness in detecting hypoglycaemic episodes of which the patient may not have been aware, potentially reducing the need for painful fingerprick glucose testing.

4) Use CGM (unblinded) to titrate medication to abolish hypoglycaemia in order to improve outpatient management and improve patient safety. The Dexcom system has an alarm to alert patients to hypoglycaemia which will be used in the unblinded phase.

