6.3 Primary endpoint

Arm 1 -

Outpatient - CGM findings reflect patient's fingerprick glucose readings

- Episodes of true hypoglycaemia (as decided by finger prick glucose testing) are captured by the CGM device

- CGM detects hypoglycaemia whilst patient is asleep

Inpatient - 72 hour fast - CGM device calls hypoglycaemia when fingerprick/lab glucoses also do

Arm 2 -

Blinded phase - CGM findings reflect patient's fingerprick glucose readings - any episodes of true hypoglycaemia (as decided by fingerprick glucose testing) are captured by CGM device

unblinded phase - CGM recordings help with titration of anti hypoglycaemic medications and this reduces overall incidence of hypoglycaemic episodes or duration of time spent in hypoglycaemic range

For patients experiencing asymptomatic hypoglycaemic episodes, a reduction in asymptomatic hypoglycaemic episodes and regaining of hypoglycaemic symptoms.

For patients with symptomatic hypoglycaemia, a reduction in symptomatic episodes.

7. Study population

Clinicians in the endocrinology department at St Bartholomew's hospital will be notified of this study and encouraged to refer forward suitable patients from their clinics.

Arm 1

Patients referred to the endocrinology department at St Bartholomew's hospital for investigation of suspected hypoglycaemia by either GPs or other clinical teams in the same or external NHS trusts will be referred onwards to the study team by the doctor that sees them for their routine clinical care.

Arm 2

Patients known to the endocrinology department at St Bartholomew's hospital with hypoglycaemia that are medically managed or who are to start medical management will be referred to the study team by the doctor that sees them for their routine clinical care.

Some patients who are found to have hypoglycaemia through arm 1 of this study will be automatically offered the chance to partake in arm 2 if they are to have medical treatment.

No vulnerable groups will be included – all patient will be able to give valid consent on their own behalf
All patients will be able to understand sufficient English to give informed consent on their own behalf.

Inclusion Criteria

Able and willing to give informed consent. No vulnerable adults will be included.
Either conventional gender, or non-binary.
Age >18 years
Any ethnicity
Any socio economic group
Medical condition as detailed above – arm 1 under investigation for possible/probable hypoglycaemia

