Patients who have been diagnosed with spontaneous hypoglycaemia which requires medical therapy will be given a CGM kit and a finger prick glucose monitoring device and glucose monitoring diary. Patients will take the standard medical therapy and perform finger prick glucose testing when they experience symptoms that they attribute to hypoglycaemia. These values will be recorded in the glucose monitoring diary. After (up to) 10 days of blinded CGM monitoring, the diary and CGM data will be reviewed. A member of the endocrine team (consultant or registrar with consultant approval) will then make changes to the medical therapy in order to abolish any remaining episodes of hypoglycaemia. Patients will then wear the CGM device in unblinded mode for up to a further 20 days (though likely to be far less) in order to facilitate further medication titrations. Patients will be asked to confirm low CGM glucose readings during this time with a finger prick glucose measurement.

The study organisers will observe the glucose data obtained from the CGM and match it with finger prick glucose readings (from glucose monitoring diaries) and lab glucose data to check for concordance.

CGM data (in conjunction with glucose monitoring diaries) will be scrutinised and compared against drug regimens to see which doses needed to be altered, or where additional medication is required.

Patients will complete a modified Clarke and Gold hypoglycaemia questionnaire at the start of arm 2. They will complete an adapted questionnaire prior to surgery for their hypoglycaemia (if indicated) or at 6 months after the start of arm 2 – whichever comes first.

9. Study procedures

Arm 1

Patients will be recruited either through attendance at endocrinology outpatients at St Bartholomew's hospital or through inpatient transfer to St Bartholomew's hospital – both with suspected diagnoses of hypoglycaemia.

If attending the outpatients department with suspected hypoglycaemia and thought to be suitable for the study, then the patient will meet a member of the study team after their outpatient appointment or they will be offered an appointment to discuss the study at a mutually convenient time. Informed consent will be obtained during this meeting.

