12.2 Method of analysis

P<0.05 will be considered statistically significant

Arm 1

Positive and negative predictive value of CGM diagnosis of hypoglycaemia as an outpatient or an inpatient vs 72 hour fast (considered the 'gold standard')

Arm 2

In each patient, comparison of number of episodes of hypoglycaemia by finger prick glucose vs CGM vs symptoms during CGM blinded phase.

Severity of hypoglycaemia excursions

Amount of time spent in the hypoglycaemic range after medication titration – as measured by area under the curve on a time vs glucose graph generated by CGM machine. Comparisons of mean hypoglycaemic frequency and time within hypoglycaemic range within patients (blinded vs unblinded phase) using paired T test.

Change in hypoglycaemia questionnaire score before/after CGMs monitoring and medication titration

Regain of symptomatic hypoglycaemia in patients with asymptomatic hypoglycaemia, reduction of symptomatic hypoglycaemia in other patients.

13. Ethics

- Informed consent

Patients will be offered the chance to partake in the study should their treating consultant feel that they meet the inclusion criteria. Declining an invitation to take part in the study or leaving at any time means that the patient will default back to standard of care investigations. Their care will not be prejudiced or compromised in any way through either taking part or not taking part in the study.

- Recruitment

Only patients under investigation/treatment for hypoglycaemia at St Bartholomew's hospital will be considered for entry to the study. Patient being treated/investigated elsewhere who wish to be considered for the study would need to have their care transferred to St Bartholomew's by their GP/current endocrinologist.

- Inclusion / exclusion criteria

Inclusion/exclusion criteria is intended to screen out patients who have conditions that may affect their blood glucose (Diabetes Mellitus, underlying hepatic pathology) or in whom CGM is not recommended (pregnancy, critical illness) or in whom hypoglycaemia may be caused by extrinsic factors such as Diabetes medication.

- Study design

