Aside from the wearing of a CGM device and completion of modified Clarke and Gold hypoglycaemia questionnaire (arm 2), all treatment is ‘standard of care’. In arm 1 (and, initially, arm 2) Patients and investigators are blinded to the CGM readouts. Patients are provided (as is usual) with finger prick glucose meters that they can use to check their blood sugar should they develop symptoms that they attribute to hypoglycaemia. The patients are therefore not disadvantaged by the ‘blinding’ process.

- Risks, burdens, and benefits

Patients will be counselled about (the few) risks associated with use of the Dexcom device, the main risks are those of infection from insertion of the probe under the skin and the risk of retained parts upon removal of the probe – and how to minimise these risks. The device is worn and as such may restrict the wearer’s choice of clothing and place some minor limitations on physical activity – mainly laying on top of the probe or engaging in close contact activities which might disrupt the probe’s positioning.

- Confidentiality

All patients recruited for the study will already be under the medical care of the endocrine team at St Bartholomew’s hospital, the study team is made up of staff from this department and they will therefore already have legitimate access to medical records and pathology results.

Any published data arising from this study will be anonymised.

Any data shared with Dexcom will be pseudonymised – each participant will receive a study number which will not be related to any of their identifiable details (name/DOB/address/NHS or hospital number).

- Conflicts of interest.

Dexcom will provide the study team with free receivers, transmitters, consumables and training in their equipment’s use. They have not had any influence on the study design, but have reviewed our design internally prior to granting approval for provision of the above equipment.

Dexcom will be allowed to share the data that we obtain, which will be pseudonymised. They will also be allowed to view the manuscript of any work (containing anonymised data) prior to submission to a peer reviewed journal, so that they can make suggestions but will not be the determining factor in the decision to submit work arising from this study for publication. This decision will reside with the study team and be based on scientific merit of the findings.

No other members of the study team have any relevant conflicts of interest.

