17.1 Devices

- Name - Dexcom G6 Mobile continuous glucose monitoring system
- Manufacturer - Dexcom
- Indication – continuous glucose monitoring, usually in Diabetes Mellitus
- CE mark status – has a CE mark under Medical Device Directive MDD 93/42/EEC as amended by 2007/47/EC
- Source of device - Dexcom

For arm 1 and the blinded portion of arm 2, the device will be worn/used in the standard way and used to monitor for hypoglycaemia. The device will be programmed so that the alarm functions which usually signal hypoglycaemia are inactivated and the screen which displays the current glucose reading will not show this information.

During the unblinded portion of arm 2, the device will be worn in the standard way with hypoglycaemia alarms active and the glucose display showing the current glucose.

- Name – Contour next ONE blood glucose monitoring system
- Manufacturer – Ascensia Diabetes care
- Indication – finger prick glucose monitoring, usually in Diabetes Mellitus
- CE mark status – has a CE mark Source of device – either through NHS trust or directly from Ascensia

Finger prick glucose testing is standard in inpatient investigation of hypoglycaemia and also in home monitoring of blood sugar in patients being treated for proven hypoglycaemia. We will additionally use prior to patient's admission for investigation of hypoglycaemia (arm 1) as a correlate for CGM data. Patients will be asked to perform a finger prick glucose measurement whenever they experience the symptoms that they attribute to hypoglycaemia

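### In the arm 2 blinded phase finger pricks follow symptoms, so the finger-prick count in section 12.2 cannot test CGM on episodes the patient is unaware of

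*Protocol*

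**What the plan says.** Section 12.2 of the Protocol sets three counts side by side for arm 2: "In each patient, comparison of number of episodes of hypoglycaemia by finger prick glucose vs CGM vs symptoms during CGM blinded phase". This serves objective 3 in section 6.1, which is to judge CGM's "effectiveness in detecting hypoglycaemic episodes of which the patient may not have been aware, potentially reducing the need for painful fingerprick glucose testing".

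The testing rule is in section 8 (Arm 2). Patients "perform finger prick glucose testing when they experience symptoms that they attribute to hypoglycaemia" and write the values in a diary. Section 13 gives the same trigger for the blinded phases: meters that patients can "use to check their blood sugar should they develop symptoms that they attribute to hypoglycaemia". Section 17.1 gives it too: "Patients will be asked to perform a finger prick glucose measurement whenever they experience the symptoms that they attribute to hypoglycaemia", although the sentence before it concerns arm 1. No scheduled finger prick is specified anywhere for arm 2. Confirming a low CGM reading by finger prick is required only once the device is unblinded (sections 8 and 9).

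Section 6.3 makes finger prick the arbiter in the blinded phase: "any episodes of true hypoglycaemia (as decided by fingerprick glucose testing) are captured by CGM device". Section 5.4 describes another use of finger pricks. It says that lack of awareness "can be overcome during the day with regular fingerprick glucose checks".

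**The concern.** Section 12.2 treats finger prick and symptoms as two methods of detection, each to be set against CGM. Under the stated rule they are not separate. A finger prick is prompted by a symptom, so a finger-prick episode is a symptomatic episode that the meter confirmed. The count has no planned way of containing an episode the patient did not feel, even while awake.

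Objective 3 is about exactly those episodes, and it looks ahead to fewer finger pricks. For patients without awareness, the practice that CGM might replace is the regular daytime checking described in section 5.4. The blinded phase does not call for such checks. Lows seen only by CGM also have no reference value in that phase, so real lows and sensor error add to the CGM count alike. If the report reads a CGM excess as better detection, the testing rule will have produced much of that result.

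**Working it through.** The Protocol gives no figure for this analysis, so there is none to reproduce. Section 12.1 fixes 30 patients as a pilot, without a power calculation.

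**1. Logic of the stated rule.** Finger-prick episodes are a subset of symptomatic episodes, so the finger-prick count of unaware episodes is 0. The CGM count of such episodes is 0 or more. Hence P(CGM < finger prick) = 0 for unaware episodes, whatever the sensor's accuracy. A sensor that never reads low without symptoms ties at 0 to 0.

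**2. Room for false lows.** Section 5 gives quarter-hourly readings (96 a day), section 7 a blinded phase of up to 10 days, and section 11 a discarded first 2 hours (8 readings). With one warm-up, R = 96 × 10 − 8 = 952 readings. Let f be the chance that a reading is falsely low. The Protocol does not give f, so a range is assumed. With independent readings, P(at least one false low) = 1 − (1 − f)^952:

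| f (assumed) | P(at least one) |
|---|---|
| 0.01% | 9% |
| 0.05% | 38% |
| 0.1% | 61% |
| 0.5% | 99% |

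Sensor errors are likely to cluster, which would lower these chances. Section 5 reports 93.5% of readings within 30% of reference below 3 mmol/L. That shows the sensor has error in this range, but it is not a false-low rate.

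**3. Does the direction of the result tell a good sensor from a bad one?** Assume Poisson counts per patient: a mean of U unaware episodes, sensitivity s and a mean of F false episodes. Under the stated rule, P(CGM > finger prick on unaware episodes) = 1 − exp(−(sU + F)). Simulation of 200,000 patients per scenario agrees:

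| Sensor (assumed) | U | s | F | P(CGM > finger prick) |
|---|---|---|---|---|
| Good | 5 | 0.9 | 0.2 | 99% |
| Detects nothing | 5 | 0 | 2 | 87% |
| No unaware episodes exist | 0 | 0 | 5 | 99% |
| Never reads low | 5 | 0 | 0 | 0% (tie) |

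**4. Total counts, which are what 12.2 compares.** Let a be the share of true lows that are asymptomatic. Assume no false CGM lows, and that every symptomatic low is pricked and confirmed. The expected ratio of CGM to finger-prick counts is s/(1 − a). For assumed s of 0.85 to 0.95:

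| a (assumed) | Ratio |
|---|---|
| 0% | 0.85 to 0.95 |
| 10% | 0.94 to 1.06 |
| 20% | 1.06 to 1.19 |
| 40% | 1.42 to 1.58 |
| 60% | 2.13 to 2.38 |
| 80% | 4.25 to 4.75 |

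CGM trails when a < 1 − s, that is, below 5% (s = 0.95) to 15% (s = 0.85).

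**5. Would extra pricks repair a count comparison?** Suppose symptom-independent pricks caught 25% of unaware episodes (assumed). The sensor in step 3 with s = 0 and F = 2 would then record fewer unaware episodes than finger prick in about 24% of patients, but still more in about 55%. Extra pricks let CGM lose, but episode counts remain a poor measure. Pairing by time is needed.

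**The case against.** The strongest reply is that the damage is narrow. The blinded-phase endpoint in section 6.3 asks whether finger-prick-confirmed episodes are captured by CGM, and CGM can fail that. Section 8 also matches CGM with diary and laboratory values for concordance. This stands: for symptomatic episodes the data remain informative.

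A reader might infer that the comparison is circular and that CGM must win it. The Protocol does not support that. CGM plays no part in defining the finger-prick result, so the fault is verification that depends on symptoms. On unaware episodes CGM cannot lose, but it can tie. On the total counts in 12.2 it can trail when few lows are asymptomatic.

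It can also be said that extra finger pricks are not forbidden. Section 17.1 calls home testing standard in treated patients, section 15.2 draws on the meters as well as the diaries, and section 17.3 has the diary record symptoms with each reading. Some symptom-free readings may therefore exist. They would be unplanned, and their number and timing are unknown.

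Confirmation in the unblinded phase does bear on whether CGM lows are real. It checks only readings CGM has already called low, and in a different phase. Arm 1 inpatients have routine finger pricks and twice-daily venous glucose, but in another setting.

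Finally, this is a pilot and objective 3 speaks only of a potential reduction in finger pricks. That limits the harm, but the comparison should still be able to come out against the device on the question it is meant to answer.

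**Conclusion.** The point holds for unaware episodes. In the arm 2 blinded phase the finger-prick count is essentially the confirmed subset of symptomatic episodes, and it cannot serve as an independent comparator for objective 3. CGM-only lows in that phase are unverified. A statistical analysis plan cannot cure this, because it cannot recover reference values that were never collected.

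On size, a CGM excess on unaware episodes would appear in about 87% of patients with a sensor that detects none of them and in about 99% with a good one, so the direction of the result says almost nothing about validity. These percentages rest on assumed episode and error rates. The zero chance of losing rests only on the testing rule as written and on patients making no other finger pricks.

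**What to change.** In section 12.2 (Arm 2), label the count 'finger-prick-confirmed symptomatic episodes' and restrict the CGM versus finger-prick comparison to those episodes. Report CGM-only lows descriptively as unverified. State that a CGM excess will not be used as evidence of better detection or as grounds for reducing finger-prick testing, and align objective 3 with this. The cost is wording only.

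If objective 3 is to stay a comparison, add to section 8 some blinded-phase finger pricks at waking times not chosen by symptoms, and mark each diary entry as scheduled or symptom-triggered. In 12.2, compare each scheduled reading with the time-matched CGM value (agreement, sensitivity, false lows) rather than comparing episode counts. The meter and diary are already supplied, so the cost is a small burden for up to 10 days. Two limits remain. Nocturnal lows stay unverified, and patients may act on a low found at a scheduled check, which could alter the frequency that objective 3 records.

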Arm 2 – on medical therapy for established hypoglycaemia

Exclusion criteria

Unwilling or unable to give consent
Unable to speak sufficient English to give consent and understand study requirements
Age<18
Lack of capacity to consent
Underlying hepatic condition
Current excessive alcohol consumption (men regularly consuming >50 units/week, women >35 units/week)
Diabetes Mellitus
Current use of Diabetic medication or insulin
Currently pregnant
Any patient on haemo or peritoneal dialysis

Length of study participation

Arm 1 - investigation of hypoglycaemia - maximum of 10 days of monitoring (5 days as an outpatient, max 5 days as an inpatient).
Arm 2 - evaluating anti hypoglycaemic drugs - maximum of 10 days of initial monitoring (investigator and patient blinded to CGM results), then up to a maximum of a further 20 days (unblinded) monitoring, likely to be far less than this though.

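### Section 12.2 names time in the hypoglycaemic range as an arm 2 outcome but measures it by an area under the glucose curve, which is not a time

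*Protocol*

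**What the plan says.** The arm 2 list in Protocol Section 12.2 contains "Amount of time spent in the hypoglycaemic range after medication titration", followed by how it is to be obtained: "as measured by area under the curve on a time vs glucose graph generated by CGM machine". No baseline or threshold for the area is given.

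The next sentence sets the test: "Comparisons of mean hypoglycaemic frequency and time within hypoglycaemic range within patients (blinded vs unblinded phase) using paired T test". The significance level at the head of the section is "P<0.05 will be considered statistically significant".

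Depth has its own entry in the same list, "Severity of hypoglycaemia excursions", with no measure attached.

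The analysis serves the arm 2 unblinded-phase endpoint in Section 6.3, under which CGM-guided titration "reduces overall incidence of hypoglycaemic episodes or duration of time spent in hypoglycaemic range".

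Section 7 (Length of study participation) allows up to 10 days of blinded monitoring, "then up to a maximum of a further 20 days (unblinded) monitoring, likely to be far less than this though".

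**The concern.** The quantity named is a duration and the quantity measured is an area. The protocol fixes this explicitly, so it is not a detail left open for an analysis plan.

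If the stated measure is carried into the paired comparison, a change in the depth of episodes will be reported as a change in the time spent in them. The sign of that change can depend on which area the analyst takes. Conversely, a real difference in duration can be hidden by an opposite difference in depth. Either would misreport a listed arm 2 endpoint.

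**Working it through.** The protocol gives no figure to reproduce, so the check is one of units followed by small worked examples.

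**Units.** The axes are time and glucose. Area = glucose × time, in mmol/L·min or mmol/L·h. No ordinary choice of baseline turns this into minutes.

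**Assumed inputs.** Section 12.2 attaches no threshold to the CGM outcome. I use 3.0 mmol/L, one of the glucose values in the Introduction's account of device accuracy. Episode shapes and the 5.0 mmol/L background are invented for illustration and are not estimates for this trial.

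**Same time, different depth.** A flat 60-minute episode has its plateau raised from 2.0 to 2.5 mmol/L. The true change in time is 0%.

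| Measure | Before | After | Change |
|---|---|---|---|
| Time below 3.0 (min) | 60 | 60 | 0% |
| Area down to zero within the episode (mmol/L·min) | 2.0 × 60 = 120 | 2.5 × 60 = 150 | +25% |
| Area between threshold and trace (mmol/L·min) | (3.0 − 2.0) × 60 = 60 | (3.0 − 2.5) × 60 = 30 | −50% |

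**Different time, same area below threshold.**
- 60 min at 1.8: (3.0 − 1.8) × 60 = 72.
- 120 min at 2.4: (3.0 − 2.4) × 120 = 72.
- In hours, 2 h at 2.8, 1 h at 2.6 and 0.5 h at 2.2 each give 0.4 mmol/L·h, although durations differ fourfold. Episodes of the same depth below the threshold give the same 0.4 at thresholds of 2.2 and 3.9.

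**Whole area under a 24-hour trace.** With the trace at 5.0 outside the episode, total area = 24 × 5.0 − duration × (5.0 − plateau).
- 2 h at 2.8: 120 − 4.4 = 115.6 mmol/L·h.
- 1 h at 2.6: 120 − 2.4 = 117.6.
- 0.5 h at 2.2: 120 − 1.4 = 118.6.

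This total is mostly normal glucose and, in these three traces, moves in the opposite direction to time in hypoglycaemia.

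**Limit on direction.** The area to zero does not always fall as episodes deepen. Take V-shaped episodes with a slope of 0.05 mmol/L per min below 3.0. Duration = 2 × (3.0 − nadir)/0.05, area to zero = duration × (3.0 + nadir)/2, and area below threshold = duration × (3.0 − nadir)/2.

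| Nadir (mmol/L) | Duration (min) | Area to zero | Area below threshold |
|---|---|---|---|
| 2.5 | 20 | 55 | 5 |
| 2.0 | 40 | 100 | 20 |
| 1.5 | 60 | 135 | 45 |

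Both areas rank these episodes as time does, because depth and length rise together. The proportions differ: a threefold range in time becomes ninefold in area below threshold (45/5).

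**Scale for the replacement.** At a constant 60 min per day below threshold, total minutes are 60 × 10 = 600 over 10 blinded days, and 60 × 5 = 300 or 60 × 20 = 1200 over 5 or 20 unblinded days. As a share of wear time each is 60/1440 = 4.2%.

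**The case against.** The strongest reply is that the harm is conditional. The area clause belongs to one list item. The sentence that specifies the t test speaks of time in range without mentioning area, so an analyst could compute true time and satisfy Section 6.3. That is correct. But two adjacent sentences would then use different quantities for the same outcome, and the only measure stated would be the one set aside.

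Second, limiting the item to the hypoglycaemic range suggests that area below a threshold was meant. On that reading the area cannot rise when only depth improves, so the +25% result depends on a less likely reading. This also stands. Area below threshold is still not a time, however, and the 72 versus 72 example uses that more favourable reading.

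Third, flat episodes are a selective choice. In the V-shaped example, area and time agree in rank. The examples therefore show what can happen, not what is likely here.

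Fourth, the threshold and the handling of wear time are ordinary analysis-plan detail, and unequal phase length would affect total minutes too. Agreed: these bear on how to write the replacement and are not separate errors.

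Finally, this is a pilot of 30 patients, and duration is one of two alternatives in Section 6.3. That limits the impact, but the outcome definition still has to measure what it names.

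**Conclusion.** The point holds. Section 12.2 fixes as its measure of time a quantity that is not a time, and nothing elsewhere in the protocol converts it into one. With time unchanged, the illustrations give changes of +25% or −50% depending on the reading. With area unchanged, durations differ twofold or fourfold. These sizes rest on assumed thresholds and episode shapes; the mismatch in units rests on no assumption.

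The consequence is confined to the time-in-range outcome and its paired comparison, and arises there only if the stated measure is used. Episode frequency is unaffected and no sample size depends on it. It should be fixed before analysis, and the retained CGM download makes that possible.

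**What to change.** Replace the area wording in Section 12.2 with: *Time in the hypoglycaemic range is the percentage of valid CGM wear time with glucose below one stated threshold, calculated the same way in the blinded and unblinded phases.* The sponsor must state the threshold. A percentage is preferable to total minutes because the phases run for up to 10 and up to 20 days, and Section 9 lets the unblinded phase end once titration has removed most or all episodes.

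If a depth-sensitive measure is wanted, place it under the existing severity item: the area between that threshold and the CGM trace, counted only while the trace is below it, per day of valid wear.

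The cost is one reworded item, one stated analysis threshold and, optionally, a metric for the severity item. The same CGM download serves. There are no new data and little extra analysis.
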